## 4. STUDY DESIGN

### 4.1. Overall Design

This is a multi-center, randomized, double-blind, parallel-group, placebo-controlled study in subjects undergoing bunionectomy.

Subjects scheduled for bunionectomy surgery who meet all of the inclusion criteria and none of the exclusion criteria below will be enrolled and randomized.

Eligible subjects will be randomized in a 1:1:1 ratio to receive either 750 mg XG005 (low dose), 1250 mg XG005 (high dose), or placebo. Randomized subjects will receive drug per their treatment allocation as follows:

- 60 minutes prior to surgery, then
- Every 12 hours ( $\pm$  10 minutes) after the first dose for 72 hours.

Subjects and all study staff performing study assessments will be blinded to treatment allocation. To maintain the blind, a total of 5 tablets will be administered to each treatment group: 5 identical blue tablets (low or high dose XG005 or its placebo) at each time point.

Subjects will undergo a Screening Visit (Day -28 to Day -1), Pre-Operative Assessment (within 24 hours prior to surgery), and a Surgery/Treatment Visit (beginning on Day 1), when the following will occur:

- Study medication administered
- Surgery performed within 60 minutes of first study drug administration
- Time of end of surgery recorded (as time of last suture closed)
- Subjects domiciled in research center for at least 72 hours post-surgery
- Efficacy, safety, and PK assessments performed over 72-hour period post-surgery

“Time 0” will be defined as the start time of first dose from which subsequent 12-hour dosing times will be determined. All study efficacy, safety, and PK assessments are anchored to time of end of surgery (last suture). PK sampling timepoints correlate with the collection of the 11-pt NPRS efficacy assessments when they overlap.

Screening will include subjects’ potential placebo response by use of a pre-study personality questionnaire ([Appendix B](#)).

Subjects will be advised at Screening that if they terminate the study prior to 72 hours, it is requested that they remain in the clinic for continued collection of scheduled safety data only.

Subjects will be confined in the clinic from check-in through 72 hours post last dose to monitor subject safety. Subjects will be discharged at a reasonable hour of the day after the end of the 72-hour treatment period, which may include the morning after the end of the 72-hour treatment period.

There will be a Follow-up Visit on Day 15.

The Schedule of Assessments is shown in [Section 1.2](#).

#### 4.2. Scientific Rationale for Study Design

Preemptive administration of analgesic medication is more effective than medication given after the onset of the painful stimulus ([Error! Reference source not found.](#); [Error! Reference source not found.](#); [Ménigaux C](#), Adam F, Guignard B, Sessler DI, Chauvin M. Preoperative gabapentin decreases anxiety and improves early functional recovery from knee surgery. *Anesth Analg*. 2005;100:1394–9.). It has been suggested that the treatment before or during surgery prevents or alleviates the formation of peripheral and/or central sensitization which may reduce the development of pain for some time after surgery. In the current study, we included both preoperative and postoperative dosing to achieve maximal “preventive” analgesia that covers a wider window of opportunity to inhibit the formation of peripheral/central sensitization and treat postsurgical pain. In addition, by dosing preoperatively, it makes  $T_{max}$  match the time of anticipated onset of pain. Furthermore, the efficacy of pre- and post-operative pain relief using the combination of naproxen and pregabalin after bunionectomy surgery has been reported ([Wang et al 2010](#)). The present study is a double-blind, placebo-controlled randomized trial of preemptive analgesia with XG005, a prodrug of naproxen and pregabalin in adult patients.

The three Phase-I studies showed favorable PK characteristics of naproxen and pregabalin following administration of XG005, in particular, the  $C_{max}$  of both naproxen and pregabalin occur simultaneously following oral administration of XG005, with  $T_{max}$  at approximately 4 hours. This PK characteristic may result in simultaneous onset of drug effects (additive or synergistic) of naproxen and pregabalin that offers a great pharmacological benefit to clinical needs for acute pain treatment. Since the pain-relieving efficacy of XG005 is solely associated with the systemic exposure of naproxen and pregabalin resulted from the XG005 absorption and subsequent hydrolysis, the dose selection for XG005 in the current study is based on the considerations to match the systemic exposures of an efficacious naproxen dose and pregabalin dose. The steady status  $C_{max}$  for naproxen and pregabalin resulted from XG005 oral dosing was lower than the  $C_{max}$  from combined dosing of naproxen and pregabalin, which may indicate potential advantage on reducing side effects from each drug when dosed combined.

#### 4.3. Justification for Dose

In this study, the subjects will be randomized in a 1:1:1 ratio to receive one of two doses of XG005, or placebo. The two doses of XG005 are selected based on the plasma levels of naproxen and pregabalin previously associated with analgesic efficacy ([Lyrica®](#) (Pregabalin) Prescribing Information. (June 2011) Pfizer Inc., US.; [Naprosyn®](#) (naproxen sodium) Prescribing Information. (November 2017) Atnahs Pharma Australia Pty Ltd.; [Bockbrader HN](#),

Naproxen is rapidly and completely absorbed from the GI tract with an *in vivo* bioavailability of 95%. The elimination half-life of naproxen ranges from 12 to 17 hours. Steady-state levels of naproxen are reached in 4 to 5 days. Following oral administration of naproxen 500 mg tablets,  $C_{max}$  of 71,100 ng/mL,  $T_{max}$  of 2.3 hours, and  $AUC_{0-t}$  of 1,218,000 ng.hr/mL were observed. Similar AUC and 30% lower  $C_{max}$  of naproxen were produced by oral administration of 1000 mg of XG005 tablet (4  $\times$  250 mg XG005 tablets). In general, the clinical recommended dose ranges are 220 mg-1500 mg of naproxen for the various pain symptoms.

Two dose levels are planned in this study:

- 1) XG005 (low dose) with 750 mg XG005 BID which will deliver 375 mg BID of naproxen and 259 mg BID of pregabalin.
- 2) XG005 (high dose) with 1250 mg XG005 BID which will deliver 626 mg BID of naproxen and 433 mg BID of pregabalin.

Based on the PK modeling, 1250 mg XG005 BID will be equivalent to the exposure of naproxen at 490 mg BID and the exposure to pregabalin of 225 mg BID; 750 mg XG005 BID will result in bioequivalent to naproxen of 300 mg BID and pregabalin of 150 mg BID. So, the planned XG005 dose regimen would provide naproxen dose within the commonly prescribed dose for treating various pain indications. Pregabalin has been approved for maximum dose of 600 mg/day, though with 150 mg/day starting dose, in approved pain indications. Phase 1 studies in healthy volunteers from XG005 including dose of 1250 mg BID resulted in acceptable safety profile, with similar dizziness and somnolence incidences as reported in Lyrica label. Patient's safety will be carefully monitored in the study.

#### **4.4. End of Study Definition**

The end of study (EOS) is defined as the date on which the last subject completes the last visit (including the EOS and any additional follow-up).

The Sponsor reserves the right to discontinue the study at any time for clinical or administrative reasons.

## 5. STUDY POPULATION

### 5.1. Inclusion Criteria

A subject candidate must fulfill all of the following inclusion criteria to be eligible for participation in the study:

1. Willing and able to sign the ICF approved by the IRB.
2. Male or female aged 18–80 years.
3. Scheduled to undergo unilateral first metatarsal bunionectomy.
4. Capable of undergoing a bunionectomy under anesthesia as described in the study surgical and anesthetic protocol.
5. Weight  $>40$  kg and a BMI  $<39$  kg/m^2.
6. No additional planned surgeries other than bunionectomy during the course of the study.
7. Have negative urine drug screen for drugs indicative of illicit drug use (unless results can be explained by a current prescription or acceptable OTC medication at Screening as determined by the Investigator) and no detectable results on the alcohol test (breath or saliva) indicative of alcohol abuse at Screening, and/or prior to surgery (may be repeated if the Investigator suspects a false-positive result).  
*Note: For those subjects who test positive for THC, if they are willing to abstain from use or consumption of THC-containing products from Screening through end of the subject's participation in the study, they may be allowed to participate in the study.*
8. Biological female subjects must be non-lactating. They must also be either sterile (bilateral tubal ligation, bilateral salpingectomy, or hysterectomy), post-menopausal for at least 1 year, have a partner who is sterile, be abstinent, have a same-sex partner, use a highly effective double-contraception method (hormonal protection is insufficient), or use an FDA-approved contraceptive for greater than 2 months prior to Screening visit and commit to an acceptable form of birth control for the duration of the study and for 30 days from completion of the study.
9. Willing and able to complete the study procedures and pain scales and to communicate meaningfully in English with study personnel.
10. Negative result of COVID-19 test within 3 days before Day 1 visit.

### 5.2. Exclusion Criteria

Any of the following criteria will exclude a subject from the study:

1. **Medical condition or history** that in the investigator's opinion could adversely impact the subject's participation or safety or the conduct of the study, or interfere with the pain assessments, including the following:
  - a. Serious breathing difficulties or respiratory risk factors (including clinically significant use of opioid pain medicines and other drugs that depress the CNS) and conditions such as COPD that reduce lung function.
  - b. Clinically unstable hypertension, cardiovascular disease, or history of cerebrovascular events. Hypertension must be stable without known end organ damage.
  - c. Concurrent painful conditions that may require analgesic treatment during the study period.
  - d. History of significantly reduced hepatic function (ALT, AST, or LDH  $\geq 1.5 \times$  ULN) or renal function (creatinine  $\geq 1.5 \times$  ULN, angle closure glaucoma, or convulsive disorder).
  - e. Recent history of urinary retention.
  - f. History of gastrointestinal ulcer, bleeding, perforation, or recent surgery of gastrointestinal tract
  - g. Subject is currently taking or has taken a chronic opioid at a dose greater than or equal to 20 mg hydrocodone per day ( $\geq 20$  MEQs) more than 30 consecutive days of daily use) for pain in the 2 months prior to surgery.
  - h. Active cutaneous disease, or other disease, at the surgical site.
  - i. Peripheral vascular disease, sickle cell disease, vascular grafts, or vasospastic disorders.
  - j. Known bleeding disorder or is taking agents affecting coagulation preoperatively. DVT prophylaxis of the surgeon's choice is permitted postoperatively.
  - k. Diabetes mellitus (uncontrolled). Diabetes must be controlled without known end organ damage ( $\text{HgbA1c} < 7\%$ ).
  - l. History of malignancy in the past 2 years with the exception of squamous cell or basal cell carcinoma.
  - m. Prior bunionectomy on the index foot or other foot surgery on the index foot that could impact the surgery or data collection endpoints.
  - n. Presence of, history of or family history of keloid and/or hypertrophic scar
2. **Use of disallowed medications** at the window specified below and planned to use throughout the study period, including the following:

- a. Pain medication (opioids, NSAIDs, COX-2 inhibitors, tramadol, ketamine, clonidine, gabapentin, pregabalin, or cannabinoids) within 2 days prior to Day -1.
- b. CNS active drugs such as benzodiazepines, tricyclic antidepressants, Serotonin, and norepinephrine reuptake inhibitors (SNRIs), selective serotonin reuptake inhibitors (SSRIs), or any other serotonergic medications within 7 days prior to Day -1. The use of lorazepam and other sleep medications, except those containing analgesic properties, is permitted.
- c. Use of parenteral or oral corticosteroid(s) within 14 days prior to Day -1.
- d. Antihypertensive agent or diabetic regimen at a dose that has not been stable for at least 30 days, or which is not expected to remain stable throughout the study.
- e. Digoxin, warfarin lithium, theophylline preparations, aminoglycosides, and all antiarrhythmics except beta-blockers within 7 days prior to Day -1 and throughout the study.
- f. Current use of monoamine oxidase inhibitors (MAOIs) or use of MAOIs within the last 14 days.

3. Positive results for hepatitis B surface antigen (HbsAg) and/or hepatitis B anti-core antibody (anti-HBc) but negative results for anti-surface antibody (anti-HBs) at the Screening Visit.
4. Positive results for hepatitis C antibody unless patient received curative therapy and a negative viral load is documented.
5. Human immunodeficiency virus (HIV) infection or positive HIV serology at the Screening Visit.
6. Known positive COVID-19 viral test during screening or suspected COVID-19 infection at the Day 1 Visit
7. History of illicit drug use, or prescription medicine or alcohol abuse within the past 2 years.
8. History of opioid dependence.
9. History of NSAID-induced bronchospasm or presence of nasal polyps, history of asthma or chronic rhinitis.
10. Significant history of allergic reactions or known intolerance to naproxen, pregabalin or any gabapentinoid, or to any rescue medication used in the study, or any medication used in the surgical and anesthetic protocol.
11. Biological female subjects who are pregnant or lactating, who plan to get pregnant, or who have a positive serum pregnancy test at Screening and/or Day 1 (prior to surgery).

12. Participated in another clinical trial within 30 days, or previously participated in a clinical study with a similar investigational product.
13. Presence of severe depression as indicated by Patient Health Questionnaire (PHQ-9) total score of  $\geq 20$  or item 9 score  $> 0$  at the Screening Visit (see [Appendix H](#): Patient Health Questionnaire-9 (PHQ-9)).
14. Presence of severe anxiety as indicated by General Anxiety Disorder (GAD-7) score of  $\geq 15$  at the Screening Visit (see [Appendix I](#) General Anxiety Disorder (GAD-7)).
15. Presence of history of suicidal behavior or ideation as indicated by the Columbia-Suicide Severity Rating Scale (C-SSRS) Baseline/Screening Version at Screening Visit. (See [Appendix J](#) Columbia-Suicide Severity Rating Scale (C-SSRS) Baseline/Screening Version)

All Inclusion and Exclusion criteria must be verified by the Investigator or designee at Screening (Day -28 to Day -1) and Pre-Surgery (Day 1).

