Exclusion Criteria:	
1. Medical condition or history that in the investigator's opinion could adversely impact the subject's participation or safety or the conduct of the study, or interfere with the pain assessments, including the following:
 
 
a. Serious breathing difficulties or respiratory risk factors (including clinically significant use of opioid pain medicines and other drugs that depress the central nervous system [CNS]) and conditions such as chronic obstructive pulmonary disease (COPD) that reduce lung function)
 
b. Clinically unstable hypertension, cardiovascular disease, or history of cerebrovascular events. Hypertension must be stable without known end organ damage
 
c. Concurrent painful conditions that may require analgesic treatment during the study period
 
d. History of significantly reduced hepatic function (alanine aminotransferase [ALT], aspartate aminotransferase [AST], or lactase hydrogenase [LDH] <math>\geq 1.5 \times</math> upper limit of normal [ULN] or renal function (creatinine <math>\geq 1.5 \times</math> ULN), angle closure glaucoma, or convulsive disorder
 
e. Recent history of urinary retention
 
f. History of gastrointestinal ulcer, bleeding, perforation, or recent surgery of gastrointestinal tract
 
g. Subject is currently taking or has taken a chronic opioid at a dose greater than or equal to 20 mg hydrocodone per day (<math>\geq 20</math> MEQs) more than 30 consecutive days of daily use) for pain in the 2 months prior to surgery.
 
h. Active cutaneous disease, or other disease, at the surgical site
 
i. Peripheral vascular disease, sickle cell disease, vascular grafts, or vasospastic disorders
 
j. Known bleeding disorder or is taking agents affecting coagulation preoperatively. Deep venous thrombosis (DVT) prophylaxis of the surgeon's choice is permitted postoperatively
 
k. Diabetes mellitus (uncontrolled). Diabetes must be controlled without known end organ damage (hemoglobin A1C [HgbA1c] <math>< 7\%</math>)
 
l. History of malignancy in the past 5 years with the exception of cured skin squamous cell or basal cell carcinoma
 
m. Prior bunionectomy on the index foot or other foot surgery on the index foot that could impact the surgery or data collection endpoints
 
n. Presence of, history of or family history of keloid and/or hypertrophic scar
 
 
2. Use of disallowed medications at the window specified below and planned to use throughout the study period, including the following:
 
 
a. Pain medication (opioids, NSAIDs, COX-2 inhibitors, tramadol, ketamine, clonidine, gabapentin, pregabalin, and/or cannabinoids, etc.) within 2 days prior to Day -1.
 
b. CNS active drugs such as benzodiazepines, tricyclic antidepressants, Serotonin, and norepinephrine reuptake inhibitors (SNRIs), selective serotonin reuptake inhibitors (SSRIs), or any other serotonergic medications within 7 days prior to Day -1. The use of lorazepam and other sleep medications, except those containing analgesic properties, is permitted.
 
c. Use of parenteral or oral corticosteroid(s) within 14 days prior to Day -1.
 
d. Antihypertensive agent or diabetic regimen at a dose that has not been stable for at least 30 days, or which is not expected to remain stable throughout the study.
 

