### 6.2. Dosing and Administration

Study drug (XG005 low or high dose, or placebo) will be administered as an oral dose 60 minutes prior to surgery on Day 1 then every 12 hours for 72 hours after the time of first dose. The number and strength of active drug tablets to be administered at each dose level is shown in Table 1. Subjects randomized to placebo will receive the corresponding number of placebo tablets.

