### **6.3.4. Randomization**

The randomization schedule for each treatment group will be generated by Lotus Clinical Research, LLC (Lotus). Subjects who meet all entry criteria will be randomized before pre-surgery dosing on Day 1 by the IXR system.

Study drug kits will be dispensed by the clinical site pharmacist at each study site according to the randomization schedule.

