### **6.5.3. Concomitant Medication**

Any other concomitant medication deemed necessary for the welfare of the subject (except prohibited medications) during the study may be given at the discretion of the investigator. If a concomitant medication is taken, except for those specified in the protocol, a joint decision will be made by the investigator and the sponsor to continue or discontinue the subject based on the time the medication was administered, its pharmacology and PK, and whether the use of the medication will compromise the safety of the subject or the interpretation of the data. The investigator is responsible for ensuring that details regarding the medication are adequately recorded in the eCRF.

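### The washouts in exclusions 2a, 2b and 2c stop before Day -1, so a one-off dose on Day -1 or before study drug on Day 1 is not excluded; for naproxen this is the period of greatest carry-over

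*Combined protocol and SAP*

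**What the plan says.** Section 5.2, exclusion 2a, bars "Pain medication (opioids, NSAIDs, COX-2 inhibitors, tramadol, ketamine, clonidine, gabapentin, pregabalin, or cannabinoids) within 2 days prior to Day -1". The Synopsis list is worded slightly differently but has the same end point: "gabapentin, pregabalin, and/or cannabinoids, etc.) within 2 days prior to Day -1". Exclusions 2b (CNS-active drugs, 7 days) and 2c (corticosteroids, 14 days) also count back from Day -1 and stop there. Exclusion 2e goes further for its drugs: "all antiarrhythmics except beta-blockers within 7 days prior to Day -1 and throughout the study". The lead-in to the whole list covers use "at the window specified below and planned to use throughout the study period".

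On timing, Section 6.3.4 states: "Subjects who meet all entry criteria will be randomized before pre-surgery dosing on Day 1 by the IXR system". Section 6.2 says that study drug "will be administered as an oral dose 60 minutes prior to surgery on Day 1". Eligibility is verified at Screening and again before surgery on Day 1, against the same criteria.

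Three other provisions bear on the point:
- Exclusion 1c removes subjects with "Concurrent painful conditions that may require analgesic treatment during the study period".
- Section 6.5.3 says that for concomitant medication not specified in the protocol "a joint decision will be made by the investigator and the sponsor to continue or discontinue the subject".
- Section 6.5.4 ends participation for subjects given analgesics other than protocol rescue.

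**The concern.** A washout should cover the time closest to the first dose, when carry-over is largest. The windows in 2a to 2c cover days further back and leave out Day -1 and the pre-dose hours of Day 1.

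For 2a the drugs in question include those under test. XG005 is a prodrug of naproxen and pregabalin, and Section 1.2 (footnote l) lists both as plasma analytes. A naproxen tablet taken at home the evening before surgery puts active drug into a placebo subject at the time of first dosing. In the PK subgroup it adds naproxen that did not come from XG005. At stake are some blurring of early pain scores and of time to first rescue, and some contamination of PK concentrations.

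**Working it through.** **Reading the window.** The protocol numbers Screening as Day -28 to Day -1 and surgery as Day 1. I take Day -1 to be the calendar day before surgery.

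| Period | Named in 2a? |
|---|---|
| Day -3 and Day -2 | Yes |
| Day -1 | No |
| Day 1 up to first dose | No |

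A single unplanned dose in the last two rows falls outside the window and is not planned use throughout the study, so it meets neither part of the lead-in. The Day 1 check applies the same wording and does not change this.

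**Length of the gap.** Gap = 24 h (Day -1) + clock time of first dose. The protocol gives no clock time. Assuming 06:00 to 14:00, the gap is 30 to 38 h. Section 4.1 confines subjects from check-in but does not say when check-in occurs, so unsupervised time may be shorter.

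**Naproxen carry-over.** Inputs from Section 4.3: Tmax 2.3 h, half-life 12 to 17 h, Cmax 71,100 ng/mL after 500 mg. Assuming mono-exponential decline after Tmax, the fraction of peak remaining h hours after intake is 0.5^((h - 2.3)/half-life).

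| Intake before first dose | Half-life 12 h | Half-life 17 h |
|---|---|---|
| 12 h | 0.5^(9.7/12) = 57.1% | 0.5^(9.7/17) = 67.3% |
| 24 h | 28.6% | 41.3% |
| 30 h (start of gap, 06:00 dose) | 20.2% | 32.3% |
| 38 h (start of gap, 14:00 dose) | 12.7% | 23.3% |

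For 500 mg, the level at 12 h is about 71,100 × 0.571 = 40,600 to 71,100 × 0.673 = 47,900 ng/mL.

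If 2a ran from 2 days before Day -1 through the first dose, the latest allowed intake would be 48 h + 30 to 38 h = 78 to 86 h before dosing. The fraction remaining would then be 1.3-4.6% (78 h) or 0.8-3.3% (86 h). The documents give no pregabalin half-life, so I make no such calculation for pregabalin.

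**Sample size.** Section 9.2 states 90% power for 130 per arm at a standardized effect of 0.40, two-sided alpha 0.05. This reproduces: 89.7% by the normal approximation, 89.5% by the t-test.

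The documents do not say how many subjects would take such a dose or how much effect would be lost. Purely as an illustration, suppose a share p of subjects is affected and each loses a fraction r of the treatment difference, so that d = 0.40 × (1 - p × r):
- p = 1%, r = 25%: d = 0.399, power 89.3%.
- p = 5%, r = 50%: d = 0.390, power 88.0%.

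The largest loss shown is 89.5 - 88.0 = 1.5 percentage points. Both p and r are assumed.

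**The case against.** The strongest reply is that the lead-in was probably meant to carry the bar forward for the whole list, with 2e simply repeating it. Because 2b and 2c end where 2a does, the different wording of 2e is weak evidence of intent. A reader might infer that the sponsor meant to allow analgesics on Day -1; the documents do not support that. Nor do they support reading 2a as open to continuing home naproxen: the lead-in addresses planned use, and 1c removes most subjects likely to need it. What remains is one-off use, and for that the lead-in supplies no rule.

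Other provisions soften the consequence:
- Exclusion 1j concerns agents affecting coagulation preoperatively and sits under an investigator-opinion clause. An investigator could apply it to naproxen, but it is discretionary and would not reach pregabalin.
- Prior and concomitant medications are on the assessment schedule, so a dose would probably be recorded and could reach the joint decision in Section 6.5.3. That is case by case.
- Section 6.5.4 gives no start time. Applied from consent, it would leave the 2-day window in 2a with little purpose.
- THC-positive subjects must already abstain from Screening onward (inclusion 7), which covers part of the cannabinoid item.

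A reader might also infer hidden contamination of the PK results. That goes too far: every PK-subgroup subject has a pre-dose sample, in which naproxen carry-over would show. The subgroup is 90 of 450 subjects (20%) at one site, however, and no eligibility action is tied to that sample.

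**Conclusion.** The point stands as a minor defect: three stated windows end too early. The reading of the text is firm; the practical consequence is uncertain and probably small.

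A reader might infer that the efficacy comparison is biased. The documents do not support that. The intake comes before the first blinded dose and should fall on all arms alike, so the expected result is noise or dilution in early pain and time to first rescue. Nothing here calls for a change in sample size or alpha. The carry-over percentages rest on the protocol's naproxen figures and simple exponential decline; the power illustration rests on assumed prevalence and effect loss.

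**What to change.** In both the Synopsis and Section 5.2, carry the windows of 2a, 2b and 2c forward. For 2a: *from 2 days before Day -1 through the first dose of study drug*. Alternatively, put *through the first dose of study drug* once in the lead-in to exclusion 2. Amending 2a alone would make the silence of 2b and 2c look deliberate.

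Either version needs an exception for protocol-defined anesthetic, sedative and rescue drugs (preoperative midazolam, for example, is allowed by Section 6.5.5 but is a benzodiazepine under 2b) and for the sleep medications that 2b permits.

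The cost is a short wording change in two places. No procedure is added, because eligibility is already verified on Day 1. The downside is that a few subjects must abstain on those days or be rescheduled.
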